7.3.2 Exclusion criteria

- Patient is pregnant (all females of child-bearing potential must have a negative pregnancy test within 1 week of enrollment)
- Patient is enrolled in another study that could confound the results of this study, without documented pre-approval from a Medtronic study manager
- Patient has severe valvular heart disease as defined by hemodynamically significant valve stenosis and/or prosthetic heart valve
- Patient has existing IPG, ICD, CRT-D or CRT-P device
- Patient has severe renal impairment (eGFR <25mL/min)

7.4 Minimization of Bias

Selection of subjects, treatment of subjects, and evaluation of study data are potential sources of bias. Methods incorporated in the study design to minimize potential bias include (but are not limited to):

- Patients will be screened to confirm eligibility for enrollment in keeping with the inclusion/exclusion criteria
- Subject demographics will be collected at baseline on possible differences that may affect the study results
- To ensure a widespread distribution of data between centers, the maximum number of enrollments per center is 60 subjects
- A maximum of two heart failure events per subject will be used towards the primary objective
- Regular monitoring visits will be conducted for adherence to the CIP and to verify source data
- All study clinicians, participating site personnel, and Medtronic personnel will be trained on their respective aspects of the study using standardized training materials
- All centers will use the same version of the Clinical Investigation Plan (CIP) and electronic Case Report Forms (eCRF)
- An independent Clinical Events Committee (CEC) will be used to regularly review and adjudicate reported adverse events, healthcare utilizations and deaths

In summary, potential sources of bias that may be encountered in this clinical study have been considered and minimized by careful study design.

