14.5 Subgroup Analysis

No subgroup analysis is planned in this study.

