7.2. General Methodology

Data analysis will be performed by a Medtronic statistician or designee, and will be performed once at least 40 ADHF events (as adjudicated by the CEC) occurring at least 30 days post-Reveal LINQ implant have been obtained from subjects who received the downloaded RAMware and have data for the most recent 30 days prior to the event. No more than two events per subject will be included in the analysis, and those two events must be at least 90 days apart.

All analyses will be performed on an "As Treated" basis.

The cohort will include all enrolled subjects who received the downloaded investigational LINQ HF RAMware and experienced ADHF events at least 30 days post-implant. Subjects who do not experience ADHF events may also be included as a reference dataset for baseline readings of measurements (i.e. profile of measurements that do not precede ADHF events).

Any tests of treatment effects will be conducted at a two-sided alpha level of 0.05 unless otherwise stated.

Any change to the data analysis methods described in the protocol will require an amendment only if it changes a principal feature of the protocol. Any other change to the data analysis methods described in the protocol, and the justification for making the change, will be described in the clinical study report.

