7.6. Demographic and Other Baseline Characteristics

Descriptive statistics will be used to summarize baseline and demographic characteristics. For categorical data such as gender and New York Heart Association classification, counts and percentages will be employed, while for continuous variables such as age, means, standard deviation, quartiles, minimum, and maximum will be provided. These statistics will be provided both for all enrolled subjects and for the subset of subjects who receive a LINQ device.

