7.9.1. Hypothesis

Due to the feasibility nature of this trial, there are no hypotheses for this objective.

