7.9.4. Analysis Methods

Physiologic data (including heart rate, bioimpedance, activity, blood pressure and weight), as well as blood samples (including serum BUN, creatinine, NT-proBNP, hemoglobin, hematocrit, troponin, eGFR and electrolytes), will be collected from subjects with acute decompensated heart failure. [REDACTED]

This document is electronically controlled. Printed copies are considered uncontrolled.

Confidential

The following table lists out the RAMware features and frequency of measurements.

[REDACTED]	[REDACTED]	[REDACTED]
[REDACTED]	[REDACTED]	[REDACTED]
[REDACTED]	[REDACTED]	[REDACTED]
	[REDACTED]	[REDACTED]
	[REDACTED]	[REDACTED]
[REDACTED]	[REDACTED]	[REDACTED]
	[REDACTED]	[REDACTED]
[REDACTED]	[REDACTED]	[REDACTED]

[figure not shown]
Data will be collected from enrollment up to 3 years post-insertion. If a subject exits the study prematurely, data captured prior to exit will be included in the analysis. All data collected will be included in the analysis. Descriptive statistics (e.g. means, standard deviations, proportions) will be used to summarize the physiological and derived data recorded. Analyses will be conducted to assess changes in the physiologic and LINQ™ derived data in association with HF events.

For each subject whose device contains the downloaded RAMware, the measurements in the table above will be averaged to produce one mean value for each feature for each day. Then for subjects who experience at least one ADHF event, the daily mean values will be averaged across subjects for each day leading up to the first event per subject and each day following that event for a minimum of 14 days on either side of admission. For example, if 40 subjects have at least one ADHF event, then for each of the 14 days prior to that event, the 40 subjects' mean values for that day will be averaged. The same will be done for the 14 days following ADHF admission. This will be done for each of the features above.

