For subjects who have multiple ADHF events, plots may be produced with time on the x-axis, and daily average value for a particular feature on the y-axis, with periods in which the ADHF events occurred noted as well. The graph may have the following format. Because the lack of required follow-up visits beyond 12 months may result in ADHF events going unreported, a summary of the plot of a single subject's readings over time should include a marker at 12 months to denote the point at which required follow-up visits ended for this subject.

This document is electronically controlled. Printed copies are considered uncontrolled.

Confidential

Subjects who do not experience an ADHF event included in the analysis will have their daily data averaged across these subjects for each day post-insertion and plotted as reference for comparison with the data summaries described above.

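### The SAP compares event subjects with an unadjusted reference group but never describes the two groups at baseline, so case mix can appear as a difference in signal level

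*Combined protocol and SAP*

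**What the plan says.** Protocol Section 7.4 (Minimization of Bias) lists several methods for limiting bias, one of them being: "Subject demographics will be collected at baseline on possible differences that may affect the study results".

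SAP 7.6 summarises demographic and other baseline characteristics and fixes the populations: "These statistics will be provided both for all enrolled subjects and for the subset of subjects who receive a LINQ device". SAP 7.7 adds the percentage of subjects on cardiovascular drug classes, beta blockers among them, at each follow-up visit. Neither section splits its table by ADHF event status.

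SAP 7.9.4 builds two summaries of the device data. The first is for those with one or more ADHF events: "the daily mean values will be averaged across subjects for each day leading up to the first event per subject". The days after it are treated likewise, over at least 14 days on each side. Subjects without an analysed event have their daily data "averaged across these subjects for each day post-insertion and plotted as reference for comparison with the data summaries described above". SAP 7.2 gives the latter group its role: "Subjects who do not experience ADHF events may also be included as a reference dataset for baseline readings of measurements".

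On stratified analysis, Protocol Section 14.5 states: "No subgroup analysis is planned in this study". On inference, SAP 7.9.1 states: "Due to the feasibility nature of this trial, there are no hypotheses for this objective".

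**The concern.** The event-versus-reference plot is the only between-group comparison of device data in the readable SAP, and its groups are defined by outcome. Nothing makes them alike at baseline, and the report as planned would not show a reader how they differ. Collecting baseline data limits bias in this comparison only if the data are used in it.

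The protocol itself gives reason to expect the groups to differ. Section 4 describes HF hospitalization as one of the strongest predictors of re-hospitalization. Section 7.3.1 admits subjects through a recent admission, through intravenous therapy, or on natriuretic peptide values alone, and on both sides of an EF of 50%. Entry route and severity are therefore likely to be related to later events. They may also be related to the usual level of heart rate, heart rate variability, activity or impedance.

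At stake is what is carried forward. SAP 7.9.3 says the data will later feed hypothesis generation about which measurements predict ADHF. A standing difference in level between two kinds of patient could be taken forward as a warning sign.

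**Working it through.** **Step 1. The two curves side by side.**

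| | Event curve | Reference curve |
|---|---|---|
| Subjects (SAP 7.9.4) | At least one ADHF event, first event used | No ADHF event included in the analysis |
| Time axis | Days before and after the first event | Days since insertion |
| Value plotted | Crude mean of daily means | Crude mean of daily means |
| Matching, adjustment or own-baseline step | None in the readable text | None in the readable text |
| Column in the baseline table (SAP 7.6) | No | No |

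The time axes differ, so the plots allow a comparison of overall level but no day-by-day offset.

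**Step 2. Which reading is affected.** Write an event subject's daily value as L + c(t), where L is the subject's usual level and c(t) the event-related change. A reference subject's value is L alone.

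- Event curve minus reference = (mean L in event subjects − mean L in reference subjects) + c(t). The first term is case mix.
- Change along the event curve = c(t) − c(t₀). L cancels, provided the same subjects contribute on both days. SAP 7.4 largely secures this before the event by requiring device data for at least the 30 most recent days.

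Fixed baseline differences therefore affect the level comparison and leave the shape of the pre-event curve alone.

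**Step 3. Group sizes from the plan.** Protocol 14.2.4 and SAP 6 assume 25% of 300 subjects have an event within 12 months: 0.25 × 300 = 75 event and 225 reference subjects. The exact binomial reproduces the protocol's probabilities of at least 40 subjects with an event: above 0.9999 at 25% (stated as above 99%) and 0.912 at 16% (stated as above 91%). SAP 6 gives above 88% at 16%, which matches the probability of at least 41 (0.883). That discrepancy is a separate matter. These figures serve here only to set the group sizes.

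Standard error of a difference in means, in between-subject SD units, is √(1/n₁ + 1/n₂):
- 75 and 225: √(0.01333 + 0.00444) = 0.133
- 40 and 260: √(0.02500 + 0.00385) = 0.170

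**Step 4. Illustration of size.** The readable text gives no signal SD, no covariate–signal correlation and no covariate–event odds ratio, so the following are assumptions. One standardised baseline covariate X raises event risk (logistic, odds ratio 1.5 to 3.0 per SD, 25% with an event overall). It also correlates with signal level (r = 0.3 to 0.7). The true event-related change is zero. The signal is rX + √(1 − r²) × noise, simulated in 400,000 subjects per scenario.

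| r | Odds ratio per SD | Crude gap (SD) | Gap ÷ 0.133 |
|---|---|---|---|
| 0.3 | 1.5 | 0.113 | 0.85 |
| 0.3 | 2.0 | 0.190 | 1.42 |
| 0.3 | 3.0 | 0.272 | 2.04 |
| 0.5 | 1.5 | 0.192 | 1.44 |
| 0.5 | 2.0 | 0.318 | 2.38 |
| 0.5 | 3.0 | 0.453 | 3.40 |
| 0.7 | 1.5 | 0.279 | 2.09 |
| 0.7 | 2.0 | 0.442 | 3.31 |
| 0.7 | 3.0 | 0.639 | 4.79 |

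Adjusting for X brings the gap to within 0.005 SD of zero in every scenario. At the weak end the crude gap is lost in sampling noise; at the strong end it would look like a clear signal.

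**The case against.** The strongest answer is that the objective concerns changes in device data, and the main summary follows the same subjects across the event. A reader might infer from the missing baseline split that the pre-event change itself is confounded. Step 2 shows that it is not. This part of the objection stands and limits the point to level.

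A reader might also infer that the baseline data go unused. SAP 7.6 tabulates them and SAP 7.7 reports drug classes. What is missing is their use in the event-versus-reference comparison. Nor does Section 7.4 promise balance between subjects with and without events; it says only that demographics are collected.

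A reader might go further and conclude that case mix will show up as signal. The documents give no figure that would support this. It can show up, by an amount that depends on assumed inputs.

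Two more arguments carry weight. The study is descriptive and has no hypotheses, so no test is invalidated. For prediction, a level difference tied to severity may be genuine risk information, which adjustment would remove. Both argue for keeping the crude plot and treating any adjusted display as supplementary. They do not argue against describing the two groups.

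Finally, parts of Protocol 14.2.2 and SAP 7.9.3 and 7.9.4 are redacted. An adjustment step could lie there, so the point rests on the readable text.

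**Conclusion.** The point holds as a gap in interpretability. The SAP compares two outcome-defined groups on crude device levels and shows their baseline characteristics nowhere side by side. Case mix can therefore appear as a level difference between the curves. The size cannot be computed from the documents. The range of 0.11 to 0.64 SD (0.85 to 4.8 standard errors at 75 and 225 subjects) depends wholly on the assumed correlations and odds ratios. The event-aligned curve's shape, the sample size and the descriptive status of the study are untouched. This is a cheap improvement and does not put the primary objective in doubt.

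**What to change.** - **SAP 7.6:** add two columns to the baseline table, one for subjects with an analysed ADHF event and one for reference subjects, defined exactly as for the curves in SAP 7.9.4. Show age, sex, EF where available, prior HF events, eGFR, BNP and cardiovascular drug classes.
- **SAP 7.9.4:** keep the crude reference plot and add one supplementary display. It can be the event subjects' change from their own earlier event-free period. Alternatively, it can be a reference matched on a few fully collected baseline values and on time since insertion, which also deals with the differing time axes.
- **SAP 7.9.4:** state that crude level differences from the reference are not to be read as a pre-event signal.

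Weighting on many covariates as the main reading is not advised. Protocol 8.8 records EF only if available from the last 6 months, SAP 7.4 imputes nothing, and the event group may number only about 40.

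The cost is SAP wording, modest programming and a less precise matched curve. Protocol 8.8 already collects the baseline history, laboratory values and medications, so no new data, visits or subjects are needed.

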8 STUDY PROCEDURES

Prior to performing study related procedures, all sites must have IRB approval as well as documentation from Medtronic of center readiness.

The study by design requires a close collaboration between the heart failure specialist and LINQ™ implanters at each participating center. All implanting physicians must be experienced in the handling of Reveal LINQ™ devices.

8.1 Investigator and Site Selection Criteria

All clinical investigators managing the subject's heart failure must be qualified practitioners and experienced in the management of patients with heart failure. All implanting physicians must be experienced in the handling of Reveal LINQ™ devices.

The role of the principal investigator is to implement and manage the day-to-day conduct of the clinical investigation as well as ensure data integrity and the rights, safety and well-being of the subjects involved in the clinical investigation.

The principal investigator shall:

- Be qualified by education, training, and experience to assume responsibility for the proper conduct of the clinical investigation
- Be experienced in the management of heart failure patients.
- Disclose potential conflicts of interest, including financial, that interfere with the conduct of the clinical investigation or interpretation of results

The principal investigator shall be able to demonstrate that the proposed investigational site:

- Has the required number of eligible subjects needed within the recruitment period
- Has one or more qualified investigators, a qualified investigational site research team and adequate facilities for the foreseen duration of the clinical investigation

Center personnel training will be completed prior to participation in this clinical study.

8.2 Site Activation

During the activation process (prior to subject enrollment), Medtronic will train site personnel on the clinical investigation plan, relevant standards and regulations, if needed, informed consent and on data collection and reporting tools. If new members join the study center team, they will receive training on the applicable clinical study requirements relevant to their role before contributing to the clinical study.

Prior to performing study related activities, all local regulatory requirements shall be fulfilled, including, but not limited to the following:

- IRB approval of study documents including the current version of the CIP and Patient Informed Consent.
- Regulatory authority approval or notification (as required per local law)
- Fully executed Clinical Trial Agreement (CTA)
- Financial Disclosure
- Curriculum Vitae (CV) of investigators

- Documentation of delegated tasks
- Documentation of study training

Additional requirements imposed by the IRB and regulatory authority shall be followed, if appropriate.

In addition, all participating site staff must be trained on the current version of the CIP and must be delegated by the principal investigator to perform study related activities.

Medtronic will provide each study center with documentation of study center/investigator readiness; this letter must be received prior to subject enrollment.

8.3 Equipment Requirements

The following equipment must be available at each center to support study activities:

- Computer with high speed internet access using Microsoft Internet Explorer for data entry (version 6 or 8 or other compatible version)
- Market-released Medtronic programmer (Model 2090)
- Blood draw including BNP or NT-proBNP analysis capabilities at a certified local lab

Medtronic will supply additional Patient Assistant devices for use at the in-office follow-up visits to mark the beginning and end of the 6 minute hall walk test ONLY when the DR220 Holter is not used.

8.4 Data Collection

Clinical data are collected at designated time points throughout the study. A web-based application tool, Remote Data Capture (RDC) will be used for data entry. This tool has Electronic Case Report Forms (eCRFs) which can be accessed via an Internet browser. Data will be processed using an electronic data management system for clinical studies. Data will be stored in a secure, password protected database which will be backed up on a daily basis. Data will be reviewed using programmed and manual data checks. Data queries will be made available to study centers for resolution. Study management reports will be generated to monitor data quality and study progress. The investigator is responsible for the preparation (review and signature) of the eCRFs. At the end of the study, the data will be frozen and retained indefinitely by Medtronic. The requirements for data collection and study visit schedules are summarized in Table 6.

Table 7: Data Collection and Study Procedure Requirements at Subject Visits

STUDY PROCEDURE	Baseline	LINQ Insertion	1 Mo Visit	6 Mo and 12 Mo Office Visit	Device Transmission/HCU Monthly Call	Study Exit
Patient Informed Consent	X					
Inclusion/Exclusion Assessment	X					
Medical History	X					
Demographics	X					
Physical Exam	X		X	X		
Medication Assessment	X		X	X		X
Laboratory results	X			X		
Symptoms and Temperature (via ear is recommended)			X	X		
Final system configuration		X				
Insertion procedure information		X				
LINQ™ HF RAMware download onto LINQ™ device		X				
██████████		X				
Device Data		X	X	X	X	X
NYHA functional classification assessment			X	X		
6 minute hall walk test			X	X		
Holter (DR220) with 6 Minute Hall Walk Test (Recommended)				X*		
██████████			X	X		
LINQ™ HF RAMware removal from LINQ™ device						X
Adverse Event	As Occurs					
Healthcare Utilization						
Device Deficiency						
System Modification						
Study Deviations						
Death						

*DR220 Holter is recommended at the 6 Month Visits.

8.5 Role of the Sponsor Representatives

Medtronic personnel may provide support as required for the study under supervision of the Principal Investigator, including:

- Provide study training relevant and pertinent to the involvement of personnel conducting study activities and investigator responsibilities
- Technical support at device insertion and follow-up visits under the supervision of a study investigator, but no data entry on the case report forms, shall be performed by Medtronic personnel or their representatives at sites

- Monitoring and auditing activities

8.6 Patient Informed Consent Process

Patient informed consent (PIC) is defined as a legally effective documented confirmation of a subject's or their legally authorized representative voluntary agreement to participate in a particular clinical study after information has been given to the subject on all aspects of the clinical study that are relevant to the subject's decision to participate. This process includes obtaining a Patient Informed Consent Form and a/an Authorization to Use and Disclose Personal Health Information/Research Authorization/other privacy language as required by law that has been approved by the study center's IRB Committee and signed and dated by the subject or their legally authorized representative. A subject may only consent after information has been given to the subject on all aspects of the clinical investigation that are relevant to the subject's decision to participate. Informed consent may be given by the legally authorized representative only if a subject is unable to make the decision to participate in a clinical investigation. In such cases, the subject shall also be informed about the clinical investigation within his/her ability to understand.

Prior to enrolling subjects, each center's IRB will be required to approve the PIC Form and the Authorization to Use and Disclose Personal Health Information/Research Authorization/other privacy language as required by law. The document(s) must be controlled (i.e. versioned and/or dated) to ensure it is clear which version(s) were approved by the IRB. Any adaptation of the sample Patient Informed Consent Form must be reviewed and approved by Medtronic and the IRB reviewing the application prior to enrolling subjects.

The investigator must notify the subject or their legally authorized representative of any significant new findings about the study that become available during the course of the study which are pertinent to the safety and well-being of the subject, as this could impact a subject's willingness to participate in the study. If relevant, approval may be requested from subjects to confirm their continued participation.

Refer to Appendix D for the sample Patient Informed Consent Form Template.

Prior to initiation of any study-specific procedures, patient informed consent must be obtained from the subject or their legally authorized representative. Likewise, privacy or health information protection regulation may require subjects to sign additional forms to authorize centers to submit subject information to the study sponsor. The informed consent process must be conducted by the principal investigator or an authorized designee, and the Patient Informed Consent Form and Authorization to Use and Disclose Personal Health Information/Research Authorization/other privacy language as required by law must be given to the subject (or their legally authorized representative) in a language he/she is able to read and understand. The process of patient informed consent must be conducted without using coercion or undue improper influence on or inducement of the subject to participate by the investigator or other center personnel. The informed consent process shall not wave or appear to waive subject's legal right. The language used shall be as non-technical as possible and must be understandable to the subject and the impartial witness, where applicable.

The subject must have ample time and opportunity to read and understand the Patient Informed Consent Form, to inquire about details of the study, and to decide whether or

not to participate in the clinical study. All questions about the study should be answered to the satisfaction of the subject.

When the subject decides to participate in the clinical study, the PIC must be signed and personally dated by the subject and investigator or authorized designee, as required by the Patient Informed Consent Form. If applicable, the witness shall also sign and personally date the Patient Informed Consent Form to attest that the information in the PIC was accurately explained and clearly understood by the subject, and that informed consent was freely given.

A copy of the Patient Informed Consent Form and the Authorization to Use and Disclose Personal Health Information/Research Authorization/other privacy language, signed and dated as required by law, must be provided to the subject.

If the Patient Informed Consent Form is obtained the same day the subject begins participating in study-related procedures, it must be documented in the subject's case history that consent was obtained prior to participation in any study-related procedures. It is best practice for the informed consent process to be documented in the subject's case history, regardless of circumstance.

In the event the subject cannot read and/or write, witnessed (impartial third party) patient informed consent will be allowed, provided detailed documentation of the process is recorded in the subject's case history and the witness signs and dates the Patient Informed Consent Form. The subject should "make his mark" (sign or otherwise physically mark the document so as to indicate consent) on the PIC as well. The Patient Informed Consent Form should document the method used for communication with the prospective subject and the specific means by which the prospective subject communicated agreement to participate in the study.

The original of the signed Patient Informed Consent Form must be filed in the hospital /clinical chart and/or with the subject's study documents.

The Patient Informed Consent Form and Authorization to Use and Disclose Personal Health Information/Research Authorization/other privacy language as required by law must be available for monitoring and auditing. Any Medtronic Field personnel who support the Reveal LINQ™ insertion must be able to review the subject's signed and dated Patient Informed Consent Form and verify its completeness prior to proceeding with the LINQ™ insertion/download. In the event the Medtronic Field personnel identify the patient informed consent as being incomplete, the Reveal LINQ™ insertion will not be allowed to occur until the consent of the subject can be adequately and appropriately obtained.

